11.3.5 Analysis of Pharmacodynamics of Dihydroartemisinin

Analysis Plan for Primary Outcome

The primary outcome response variables are: temperature, serum lactate, serum glucose, acidosis, BCS, total and direct bilirubin, anemia. For each subject, values of the DHA exposure

parameters AUC_{0-12} and C_{max} values for each individual subject and treated as fixed in downstream PD analyses.

Regression methods will be used to characterize the relationship between exposure and responses, while controlling for covariates. For continuous response variables (temperature, serum lactate, serum glucose, acidosis, and anemia), linear, polynomial and E_{max} models with random effects will be considered. BCS is an ordinal scale designed to assess malarial coma in children, with possible values of 0, 1, 2, 3, 4, 5. Proportional odds mixed effects logistic regression will be used to model BCS.

Covariates will include exposure, timepoint, the interaction between exposure and timepoint, and potential confounding variables such as receipt of artesunate or artemisinin-based therapy prior to enrollment. Specific details of all models will be described in the SAP, and will include:

- The precise definition or derivation of each response variable, including potential transformations and the method for accounting for baseline values and/or associations between the baseline value and exposure
- The pre-specified covariates to be included in the model
- The procedure for choosing the covariance structure
- The alternative methods which may be considered, if model assumptions do not hold

For the analysis of the response variables included in the primary outcome, the set of p-values corresponding to tests of the effect of exposure on response at each timepoint will be adjusted using the Benjamini-Hochberg procedure to preserve the false discovery rate for the primary outcome at 0.05. The corresponding point estimates and CIs will be reported. Graphical displays of response by exposure at each timepoint will show individual measurements alongside model estimates. Individual trend plots of responses over time will also be generated for each response variable.

Analysis Plan for Secondary Outcomes

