8.1. Primary Pharmacodynamics Analysis

The primary PD analysis will be performed to assess the relationship between DHA PK exposure parameters, including AUC_{0-12} , C_{max} , $t_{1/2}$, and T_{max} , and markers of physiological dysfunction known to be associated with severe malaria. These markers of physiological dysfunction measured at planned follow-up times will be the primary outcome response variables, and will include temperature, systolic and diastolic blood pressure, serum lactate, serum bicarbonate, serum glucose, BCS, total and direct bilirubin, hemoglobin, and creatinine. Values of AUC_{0-12} , C_{max} , $t_{1/2}$, and T_{max} for each participant will be treated as fixed in all PD analyses. Details of the calculation of AUC_{0-12} , C_{max} , T_{max} , and $t_{1/2}$ can be found in the Pharmacometrics Analysis Plan.

Planned follow-up times at which the relationships between each marker of physiological dysfunction and exposure parameter will be assessed include:

- Approximately 24 hours post-first dose, for which the most recent measurement of each physiological dysfunction variable before 24 hours post-first dose will be utilized as the response;
- Approximately 48 hours post-first dose, for which the most recent measurement of each physiological dysfunction variable before 48 hours post-first dose will be utilized as the response;
- Time of completion of the final planned dose of IV artesunate, for which the first measurement of each physiological dysfunction variable after completion of the final planned dose of IV artesunate will be utilized as the response; and
- Time of first hospital discharge, for which the most recent measurement of each physiological dysfunction variable before the time of first hospital discharge will be used as the response.

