Exploratory scatterplots of each continuous primary outcome response variable will be presented by exposure parameter and timepoint beginning in [Figure 2](#) and continuing through [Figure 11](#) for the PD Analysis Population. Exploratory box plots of BCS will be presented by exposure parameter and timepoint in [Figure 12](#). Summary statistics for each continuous marker of physiological dysfunction and its change from baseline will also be presented by parameter and timepoint in [Table 13](#) for participants in the PD Analysis Population and in [Table 14](#) for the subset of the PD Analysis Population with no IV artesunate or other artemisinin-based therapy before enrollment. Proportions of participants with each BCS value will be presented by timepoint in [Table 15](#) for participants in the PD Analysis Population and in [Table 16](#) for the subset of the PD Analysis Population with no IV artesunate or other artemisinin-based therapy before enrollment.

Regression models will be fit to characterize the relationship between each primary outcome response and each exposure parameter at each of the above timepoints, controlling for covariates (given in Section 6.4). Note that receipt of oral ACT will only be considered for inclusion in analyses of the primary outcome

response variables at time of first hospital discharge. Exploratory boxplots of each continuous primary outcome response variable will be presented by covariate and timepoint beginning in [Figure 13](#) and continuing through [Figure 22](#). Exploratory stacked bar charts of BCS will be presented by covariate and timepoint in [Figure 23](#). These exploratory plots, presented for the PD Analysis Population, will be used to inform what subset of covariates will be included in each model.

Proportional odds mixed effects models will be used to assess the relationship between each exposure parameter and ordinal BCS at each timepoint. The proportional odds mixed effect model for BCS at any one of the four timepoints considered is defined as follows:

$$\text{logit}\{\tau_k(P_i, t_i, BCS_{0,i}, X_i)\} = \alpha_k + \beta_1 P_i + \beta_2 t_i + \eta^T X_i + BCS_{0,i} + b_i.$$

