In the above model, $\tau_k(P_i, t_i, BCS_{0,i}, X_i) = \Pr(BCS \leq k | P_i, t_i, BCS_{0,i}, X_i)$ represents the cumulative probability that BCS will be less than or equal to $k \in \{0,1,2,3,4,5\}$ given the covariates. The BCS level-specific intercept is represented by α_k , P_i is the exposure parameter value for the i th participant, t_i is the actual response measurement time post-first dose, $BCS_{0,i}$ is the baseline BCS for the i th participant, and X_i are the values for the i th participant of the additional covariates included in the model. The β_1 , β_2 , and η are model parameters associated with the above covariates. The term b_i represents a participant-specific random intercept, where it is assumed that b_i follow a normal distribution with mean zero and nonzero variance. For 24 hours and 48 hours post-first dose timepoints, t_i will be measured in hours post-first dose rounded to the nearest tenths place. For time of completion of the final planned dose of IV artesunate and time of first hospital discharge timepoints, t_i will be measured in days post-first dose rounded to the nearest tenths place.

The following pseudocode will be used to fit the proportional odds mixed effects models for BCS and to extract the p-value for the exposure model parameter.

```
/* Proportional odds model fit and output p-values */
proc glimmix data=dataset(where=(population=p and response=r));
*catvar = any categorical covariates included in the model;
*refvalues = the value(s) to be used as the reference level for categorical
covariate(s);
class catvar(ref=refvalues);
*baseresp = response at baseline;
*othercovars = any other covariates (including those specified in the class statement)
included in the model;
model resp = baseresp exposure time othercovars / dist=multinomial link=cumlogit;
random intercept;
by timepoint;
ods output Tests3=tests3;
run;
data tests3; set tests3(where=(effect='EXPOSURE')) ;
rename ProbF=pval;
run;
```

For the continuous primary outcome response variables, if model assumptions hold, Emax models will be fit for each primary outcome effect and each exposure parameter at each timepoint. The Emax model for primary outcome effect, E_i , is defined as follows:

$$E_i = E_{0,i} + \frac{E_{max} \times P_i^\gamma}{EC_{50}^\gamma + P_i^\gamma} + e_i,$$

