15. SUMMARY OF CHANGES IN THE CONDUCT OF THE STUDY OR PLANNED ANALYSES

Section 11.3.1 of the Protocol Version 6.0 indicates that demographic characteristics including town/village of residence will be tabulated. Participants included in the study were to be drawn from the population of children aged 6 months to 14 years residing in Tororo District, Uganda, and were seen at Tororo Hospital. As participant town or village of residence, which was collected using a free text field, within Tororo District may vary greatly, town/village of residence will not be included in summary demographics tables but will be listed in the listing of demographic information.

Section 11.3.5 of the Protocol Version 6.0 indicates that timepoint and an interaction term between exposure and timepoint will be included in all models for the primary analysis. However, because we plan to assess the relationship of interest between the primary outcome measures using separate models for each timepoint, such terms will not be included in the primary analysis models and specification of covariance structures for repeated measures will not be necessary. Actual time of response measurement may be considered for inclusion in linear and polynomial models. Section 11.3.5 of the Protocol Version 6.0 also indicates that random effects will be included in all models for the primary analysis; while random effects will be considered for inclusion in Emax models, they are not planned for linear and polynomial models.

Expanded power simulations beyond what is presented in Protocol Version 6.0 are included in this SAP.

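### The BCS model in SAP 8.1 has a participant random intercept but only one record per child, so its coefficient has no stable scale, and the printed code fits a different model

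*SAP*

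**What the plan says.** Protocol 11.3.5 states: "Proportional odds mixed effects logistic regression will be used to model BCS". That model family was to include timepoint and an exposure-by-timepoint interaction, so each child would have contributed several records.

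The SAP changes the structure. Section 15 drops the timepoint and interaction terms "because we plan to assess the relationship of interest between the primary outcome measures using separate models for each timepoint" and says that covariance structures are then not needed. It adds that random effects may be considered for Emax models but "they are not planned for linear and polynomial models". It says nothing about the BCS model.

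SAP 8.1 introduces the BCS model with: "The proportional odds mixed effect model for BCS at any one of the four timepoints considered is defined as follows". The response is a single selected value per child. At 24 hours, for example, "the most recent measurement of each physiological dysfunction variable before 24 hours post-first dose will be utilized as the response", and the other three timepoints also select one measurement. The linear predictor still ends in a term b_i, which "represents a participant-specific random intercept, where it is assumed that" the b_i are normal with mean zero and nonzero variance.

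The GLIMMIX pseudocode runs BY timepoint. Its only random-effects line is "random intercept", with no SUBJECT= option and no participant identifier in the CLASS statement.

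Tables 17 and 18 report a model parameter estimate, 95% CI and p-value for each marker, exposure parameter and timepoint. Figures 195 to 210 show the fitted BCS models.

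**The concern.** A participant random intercept separates variation between children from variation within a child. With one score per child there is no within-child replication, so b_i competes with the logistic error already in the model. If the data cannot fix the size of b_i, they cannot fix the scale of the exposure coefficient, because that coefficient is expressed relative to the total latent spread. The estimate and CI printed for BCS would then depend on where the optimiser stops.

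Text and code also disagree. A programmer who follows the code fits one model; a programmer who adds SUBJECT= to match the text fits another. The 16 BCS analyses are part of the primary analysis and are repeated in the subset without prior artemisinin therapy.

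**Working it through.** **1. Counts.** Markers × exposure parameters × timepoints = 11 × 4 × 4 = 176 primary tests (SAP Section 5). BCS accounts for 1 × 4 × 4 = 16, which agrees with Figures 195 to 210 (210 − 195 + 1 = 16). Records per child in each BCS model: 1.

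**2. The plan's own figure.** The SAP gives no figure for the BCS model. The only design figure that covers these tests is the power of 0.85 in Table 3 (176 tests, R² = 0.2, 5% non-null, N=75). Simulating simple linear regressions with Benjamini-Hochberg at 0.05 (2,500 runs) gives 0.846 to 0.851, so it reproduces. It concerns linear regression and does not bear on the random intercept.

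**3. Why the variance is nearly unidentified.** With b_i = σz and z standard normal, one record per child gives

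Pr(BCS ≤ k) = ∫ expit(α_k + βP + … + σz) φ(z) dz.

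This is close to an ordinary cumulative logit with every coefficient divided by √(1 + 0.346σ²). Equivalently, for the same fitted probabilities, β must grow by about that factor:

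- σ = 2: √2.384 = 1.54
- σ = 5: √9.65 = 3.11
- σ = 10: √35.6 = 5.97
- σ = 20: √139.4 = 11.8

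For a probit link the equivalence is exact. For the logit link specified here, only the small difference in shape between a logistic curve and its normal mixture carries information on σ.

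**4. Simulation of the model in the text.** N=75, maximum likelihood at fixed values of σ. The documents give no BCS distribution or effect size, so these are assumptions.

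| Set | Shares of BCS 0 to 5 (%) | Log-odds per SD of exposure | Data sets | σ tried |
|---|---|---|---|---|
| A | 5/5/10/15/25/40 | 0.9 | 25 | 0, 2, 5, 10, 20 |
| B | 2/2/3/5/8/80 | 0.9 | 25 | 0, 2, 5, 10, 20 |
| C | 3/4/6/10/17/60 | 0.6 | 30 | 0, 2, 5, 10 |

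| Set | Best σ: at 0 / at top / between | Median log-likelihood range over σ | Median β ratio to σ = 0 | Change in z: median (largest) |
|---|---|---|---|---|
| A | 9 / 15 / 1 | 0.29 | 11.9 at σ = 20 | 0.07 (0.39) |
| B | 14 / 8 / 3 | 0.16 | 10.8 at σ = 20 | 0.00 (0.44) |
| C | 14 / 15 / 1 | 0.29 | 1.6, 3.2, 6.1 at σ = 2, 5, 10 | 0.13 (0.45) |

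The ratios agree with the approximation in step 3.

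**5. One data set from scenario A** (z from unrounded values):

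| σ | Log-likelihood | β | SE | z |
|---|---|---|---|---|
| 0 | −95.492 | 1.05 | 0.28 | 3.68 |
| 2 | −95.923 | 1.50 | 0.44 | 3.39 |
| 5 | −96.044 | 2.93 | 0.86 | 3.39 |
| 10 | −96.050 | 5.60 | 1.70 | 3.30 |
| 20 | −96.051 | 11.07 | 3.26 | 3.40 |

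The log-likelihood moves by only 0.56 while β rises more than tenfold. The 95% CI is 1.05 ± 1.96 × 0.28 = 0.50 to 1.60 at σ = 0 and 5.60 ± 1.96 × 1.70 = 2.27 to 8.93 at σ = 10. These intervals do not overlap, yet z hardly changes.

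**6. The code as printed.** Without SUBJECT= there is one intercept for the whole data set, confounded with the α_k. Fitting that version outside SAS (one data set) gave β = 0.968 with no random effect and 0.968 to 0.972 for SDs of 0.1 to 2. The likelihood was highest at zero variance, so there is no inflation.

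**The case against.** The strongest reply is that nothing decisive changes. The SAP says its pseudocode will be used, and that code does not inflate the coefficient. Even under the model in the text, the primary decisions run through p-values, and those are nearly invariant because estimate and SE scale together. Both statements stand. They reduce the consequence to the reported estimates and CIs and to the mismatch between text and code. Near-invariance is not exact, however. In a further 30 data sets under the assumptions of set C, the likelihood-ratio z at σ = 10 differed from that at σ = 0 by a median of 0.09 and at most 0.30, and 2 of the 30 crossed p = 0.05.

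Some stronger readings are tempting but not supported:

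- **Inflated BCS odds ratios.** Table 17 reports a model parameter estimate; the SAP plans odds ratios only for parasite clearance by Day 2 (Table 27).
- **Strict non-identifiability.** That holds for a probit link. With the logit link, σ is formally identified, though very weakly.
- **Section 15 dropped the other random effects for this reason.** It gives separate models as the reason for omitting timepoint terms and covariance structures. Its sentence on random effects gives no reason and keeps them as an option for Emax models.
- **Failed fits will change the number of tests.** No failure rate has been shown.
- **Inflation by factors in the hundreds.** Results of that size come from coarse quadrature at very large σ, which overstates the likelihood there, and should not be relied on.

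**Conclusion.** The BCS model is wrong as written. It contains a variance that one record per child cannot estimate in practice, and the printed code does not fit it.

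If the text is followed by maximum likelihood, the BCS exposure coefficients and CIs in Tables 17 and 18 have no stable scale: about 1.6, 3 and 6 times the ordinary value at σ of 2, 5 and 10, with almost no likelihood to choose between them. If the code is followed, the random effect is redundant and the coefficient is not inflated. In either case the 16 BCS p-values and the Benjamini-Hochberg result are largely unaffected. The damage is to primary estimates, intervals and reproducibility, not to error control.

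The sizes rest on N=75, three assumed BCS distributions, assumed effects of 0.6 and 0.9 log-odds per SD, and maximum likelihood. GLIMMIX was not run, and the SAP names no estimation method for this model. That there is one record per child in each model, and that text and code differ, follows from the documents alone.

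**What to change.** In SAP 8.1, delete b_i and its description from the BCS model and remove the RANDOM statement from the code. Fit ordinary proportional-odds logistic regression at each timepoint with baseline BCS, exposure, actual measurement time and the selected covariates, using PROC LOGISTIC or GLIMMIX without RANDOM. Rename the model accordingly, and state in Section 15 that the random effect in Protocol 11.3.5 is also dropped for BCS because each model has one record per child.

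The cost is one model term, one line of code and a sentence in Section 15; no data collection changes. If a mixed model is wanted for its own sake, the timepoints would have to be pooled with participant as the subject. That would reverse the SAP's choice of separate models and need fuller specification.

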Sample sizes considered in these simulations included 100 or 80 participants. These original simulation results indicate that the target sample size of 100 participants provides >90% power for detecting simple linear relationships for 24 or 48 tests with an underlying R^2 of at least 0.2, if the proportion of non-null relationships among those tested is at least 5%. If at least 80 participants complete follow-up for the primary outcome measure, power for the same scenario is approximately 88%.

However, at the end of the planned enrollment period of 6 months, only 46 participants had been enrolled in the study. Further simulations were performed under the same settings described above with smaller sample sizes considered. These results are also provided in Table 3. These simulation results indicate that if at least 70 participants complete follow-up for the primary outcome measure, power for detecting simple linear relationships for 24 or 48 tests with an underlying R^2 of at least 0.2, if the proportion of non-null relationships among those tested is at least 5%, is $\geq 80\%$.

Additionally, given that there are eleven markers of physiological dysfunction, four exposure parameters, and four timepoints (see Section 8.1) of interest, the total number of possible hypothesis tests for all of these relationships is 176. Further simulations were performed under the same settings described above with 176 tests and sample sizes of 75, 80, or 90 participants considered. These results are also provided in Table 3. These simulation results indicate that if at least 75 participants complete follow-up for the primary outcome

measure, power for detecting simple linear relationships for 176 tests with an underlying R^2 of at least 0.2, if the proportion of non-null relationships among those tested is at least 5%, is greater than 80%.

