6.8. Multiple Comparisons/Multiplicity

The primary analysis involves assessing multiple exposure-response relationships measured at multiple timepoints, which can be framed as a series of hypothesis tests to evaluate these potential relationships. To accommodate the multiple hypothesis tests in the primary analysis, the set of p-values corresponding to tests of the effect of exposure on response at each timepoint will be adjusted using the Benjamini-Hochberg procedure to preserve the false discovery rate for the primary outcome at 0.05. There are no adjustments for multiple comparisons planned for secondary or exploratory analyses.

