/* Fit Logistic Regression and Estimate Odds Ratio for Exposure Parameter */
proc logistic data=dataset(where=(population=p));
*catvars = any categorical covariates included in the model;
*refvalues = the value(s) to be used as the reference level for categorical
covariate(s);
class catvars(param=ref ref=refvalues);
*othercovars = any other covariates (including those specified in the class statement)
included in the model;
model D2totcl (event='Yes') = exposure othercovars;
by timepoint;
oddsratio exposure;
```

```
ods output oddsratiostwald = orest;
run;
```

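### If about 4 or fewer of 75 children score below 5, the Wald p-value specified for the Blantyre Coma Score (BCS) misses the planned Benjamini-Hochberg cut-off whatever the exposure effect; use a likelihood-ratio or score test

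*SAP*

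**What the plan says.** SAP 8.1 fits a separate cumulative-logit model for BCS for each exposure parameter at each timepoint, and supplies code to "fit the proportional odds mixed effects models for BCS and to extract the p-value for the exposure model parameter". The code line is "ods output Tests3=tests3", from which ProbF is kept. That is a Wald-type F test: the squared estimate over its variance. No score, likelihood-ratio, exact or penalised test is named.

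SAP 5 counts "eleven markers of physiological dysfunction, four exposure parameters, and four timepoints" and concludes that "the total number of possible hypothesis tests for all of these relationships is 176". BCS is one of the eleven markers. Under SAP 6.8 the primary p-values are "adjusted using the Benjamini-Hochberg procedure to preserve the false discovery rate for the primary outcome at 0.05".

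The 176-test power statement in SAP 5 applies "if at least 75 participants complete follow-up for the primary outcome" measure and concerns "power for detecting simple linear relationships for 176 tests with an underlying R^2 of at least 0.2". No ordinal test was simulated.

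Neither document gives or assumes a BCS distribution, and SAP Table 15 is an empty shell. SAP 8.1 ends its model section with a general clause allowing other models or transformations when assumptions fail. It says nothing about sparse BCS levels, separation or non-convergence.

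**The concern.** The BCS scale stops at 5. SAP 3.3 lists 15 qualifying signs, of which BCS below 3 is one, and a single sign suffices, so a child can enter with a score of 5. Two of the four timepoints in SAP 8.1 are the first value after the last planned IV dose and the last value before discharge. Small counts below 5 are therefore foreseeable at some timepoints.

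With few such children, a strong exposure effect pushes the data towards separation. The slope and its standard error then grow together, and the Wald statistic stalls or falls (the Hauck-Donner effect). BCS is the only coma measure among the primary markers. A result reported as not significant could then reflect the choice of test rather than the absence of a relationship.

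**Working it through.** **Inputs.** From SAP 5, 6.8 and Table 3: 11 markers, 4 exposures, 4 timepoints; BH at 0.05; N = 75; R² = 0.2; 5% or 10% of tests non-null. The number of children below 5, written k, is not in the documents and is assumed over a range.

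**Family and cut-offs.** 11 × 4 × 4 = 176 tests, of which 4 × 4 = 16 (9.1%) are BCS. The BH cut-off at r rejections is 0.05 × r / 176:
- r = 1: 0.00028
- r = 9 (5% of 176 = 8.8): 0.00256
- r = 18 (10% of 176 = 17.6): 0.0051

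**The plan's own figure.** Simulating independent simple linear regressions with BH reproduces Table 3 for 176 tests. At 5% non-null the results are 0.852, 0.885 and 0.925 for N = 75, 80 and 90 (stated 0.85, 0.88, 0.93). At 10% they are 0.899, 0.924 and 0.953 (stated 0.90, 0.92, 0.96).

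**Smallest attainable Wald p-value.** The search covered which k of 75 children score below 5, in a logistic model of below 5 versus 5 with exposure only.

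| k | normal exposure | lognormal exposure |
|---|---|---|
| 1 | 0.130 | 0.069 |
| 2 | 0.044 | 0.021 |
| 3 | 0.020 | 0.010 |
| 4 | 0.0105 | 0.0057 |
| 5 | 0.0060 | 0.0034 |
| 6 | 0.0036 | 0.0021 |
| 8 | 0.0015 | 0.0009 |
| 10 | 0.0007 | 0.0004 |
| 15 | 0.00017 | 0.00011 |

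Up to k = 4, no data pattern reaches 0.00256 or 0.0051. From about 6 to 8 the rank-9 cut-off is attainable; 0.00028 needs about 12 to 15. By contrast, the likelihood-ratio p-value at complete separation is 1.8e-5 for k = 2 and 5e-7 for k = 3.

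With the scores below 5 spread over two or three levels in a proportional-odds model (normal exposure), the smallest p-value is 0.010 to 0.012 for k = 3, 0.0017 to 0.0024 for k = 5 and 0.00017 for k = 8.

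**Effect size.** Latent R² = 0.2 corresponds to a log-odds of √[(0.2/0.8) × π²/3] = 0.907 per SD of exposure.

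**Rejection rates.** N = 75, cut-off 0.00256, binary model, Wald / likelihood ratio. Here k is the expected count, so realised counts vary.

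| Expected k | 0.9 per SD | 1.5 | 2.5 | 4 | 8 |
|---|---|---|---|---|---|
| 3 | 0% / 10% | 1% / 29% | 2% / 58% | 0% / 82% | 0% / 92% |
| 5 | 2% / 14% | 7% / 41% | 14% / 81% | 6% / 95% | 0% / 98% |
| 8 | 7% / 23% | 33% / 65% | 48% / 93% | 31% / 99% | 1% / 100% |
| 10 | 13% / 32% | 46% / 74% | 67% / 97% | 53% / 100% | 7% / 100% |

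Wald rejection rises and then falls as the effect grows. With exactly 8 below 5 at 0.9 per SD, Wald rejects 6% and the score or likelihood-ratio test 18-22%. The score test's null rate at nominal 0.0025 was 0.001 to 0.004. The likelihood-ratio test was slightly liberal at k = 3 (0.007).

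**The case against.** **The distribution is unknown.** A reader might infer that BCS sits at its ceiling at every timepoint. The documents do not show that. The 24-hour response is the most recent value before 24 hours and BCS is required only daily, so it may come from Day 1. Impaired consciousness and coma are both entry signs. This stands, and the point is therefore conditional.

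**BH has no single cut-off.** It runs from 0.00028 to 0.05. At k = 4 the smallest p-values pass only with 0.0057 × 176 / 0.05 = 20.06, so 21, to 0.0105 × 176 / 0.05 = 36.96, so 37, rejections. At k = 5 the same sum gives 12 to 22. This stands: impossibility is tied to the plan's own shares of true effects.

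**The SAP's model is ordinal.** Binary figures discard the ordering. A small simulation (250 trials per setting, three levels below 5, slopes 1.5 and 2.5, cut-off 0.0025) gave Wald 10-14% ordinal against 0-0.8% binary at k = 5, and 44-84% against 26-54% at k = 8. So the binary figures overstate the loss where scores are spread. The limit near 4 is also approximate: a check combining spread scores with skewed exposure could pass the rank-9 cut-off at k = 4, but only when the affected children lay in the long upper tail of exposure. When they lay at the low end, the limit was tighter.

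**Strong effects are outside the plan.** At 0.9 per SD both tests are weak, because events are few. This stands: changing the test does not rescue power.

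**The SAP has partial safeguards.** BCS is tabulated and plotted, estimates carry 95% intervals, the study is exploratory, and the general clause allows other models. None of this names sparse BCS data or changes the stated test.

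**Conclusion.** The point holds conditionally. If about 4 or fewer of 75 children score below 5 at a timepoint, the specified p-value cannot fall below about 0.006 to 0.01 in a two-level, exposure-only model. It then misses 0.00256 whatever the exposure effect. With about 5 to 10 below 5 the test works but is weaker than the likelihood-ratio or score test, and increasingly so for strong effects. Neither test brings BCS near the stated 85%, which was derived for linear relationships only.

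This rests on assumed counts below 5 and on models without baseline BCS, time, other covariates or the random intercept.

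Two further inferences are tempting but unsupported. One is that BCS models that cannot be fitted inflate the BH denominator. The SAP applies BH to the set of p-values, a failed model yields none, and 176 is described as the number of possible tests. The other is that the Wald limits for Day-2 parasite clearance share the problem. That outcome is secondary and outside BH, and nothing in the documents suggests that few children remain uncleared.

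**What to change.** In SAP 8.1, take the BCS exposure p-value from a likelihood-ratio, score or permutation test in a maximum-likelihood proportional-odds model that keeps the ordinal levels. The score or permutation version is safer at the smallest counts. Omit the participant random intercept: each model has one record per child, and SAP 15 already treats timepoints in separate models. Report profile-likelihood or Firth intervals.

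State in advance a minimum number of children below 5 for a BCS test to enter the BH family. Below that number, list the children descriptively. The rule uses BCS counts alone, so it can be fixed before exposure is examined. SAP 5 should also say that Table 3 does not cover the BCS tests.

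The cost is a few lines of text and code, slightly more computing, and a small departure from the stated mixed model. No new data are needed.
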